4.1.3 Exploratory Analyses

4.1.3.1 Subgroup Analysis: Impact of Demographic Factors and Center

With the aim to provide the same standards and granularity in terms of investigational results across VRVg studies, and comply with health authorities requirements (3), the possible influence of several covariates on the safety and immunogenicity results will be studied using descriptive statistics. Thus, the main immunogenicity and safety parameters will be described according to gender, age group, ethnicity (only if more than 5% of subjects had different ethnicity), race (only if more than 5% of subjects had different race), and center.

Race and ethnicity will be defined according to current guidelines (3).

Age groups are the following ones: ≥ 18 to 40 years, ≥ 41 to 64 years, and ≥ 65 years.

These exploratory analyses will be performed on the FASI (for immunogenicity) or SafAS population (for safety).

In case of any safety signal detected in the VRVg-2 vaccines, a statistical comparison will be performed between VRVg-2 groups (VRVg-2+HRIG and/or VRVg-2) and each of the control groups with a Fisher exact test in order to check for statistical significance (alpha=0.05, two sided).

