2.2 Secondary Objective(s)

Safety

To describe the safety profile of VRVg-2 versus Verorab and Imovax Rabies vaccines when co-administered with HRIG, as well as that of VRVg-2, after each vaccine injection.

Immunogenicity

- 1) To demonstrate that the proportion of subjects in the VRVg-2 + HRIG group achieving an RVNA titer ≥ 0.5 IU/mL at D28 is at least 95%.
- 2) To describe the immune response induced by VRVg-2 versus Verorab and Imovax Rabies vaccines when co-administered with HRIG, as well as that induced by VRVg-2, at D14 (7 days after the third injection), at D28 (14 days after the fourth injection), and at D42 (14 days after the last injection).

The endpoints for the secondary objectives are presented in [Section 9.2.1.2](#) (safety) and [Section 9.2.2.1](#) (immunogenicity).

3 Investigators and Study Organization

This study will be conducted in 2 centers in France, with one Principal Investigator (PI) per center. One of the 2 PIs will be the Coordinating Investigator and will coordinate with the PI from the other site and any sub-investigators at the individual sites.

Details of the study centers, the Investigators at each center, and the Coordinating Investigator are provided in the “List of Investigators and Centers Involved in the Trial” document.

Monitoring and Data Management activities will be conducted by a Contract Research Organization (CRO), under the responsibility of the Sponsor.

No independent data monitoring committee is planned to be set up for this trial as the investigational vaccine was shown to be safe and well-tolerated in a previous clinical study conducted with VRVg-2 (ie, VRV11), and several other clinical studies conducted with the precedent formulation VRVg-1 (ie, VRV01, VRV08, VRV02, VRV04, VRV06, and VRV11). It is also to be noted, that VRVg constitutes an improvement of Verorab in terms of the purification process, and technological innovation in vaccine manufacturing and characterization. The development of VRVg is being

[REDACTED] Consequently, the wide post-marketing experience of Verorab vaccine and adequate safety profile is considered supportive of VRVg safety profile.

There will be an internal SMT review performed on a regular basis as part of an ongoing safety review. This SMT led by the Global Safety Officer (GSO) includes core representatives from the Global Pharmacovigilance (GPV) Department and from the Clinical Department. Reviews will be performed in a blinded manner.

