4.1.2.2 Statistical Methods

The superiority testing will be demonstrated if the lower limit of the 95% CI of the proportion, calculated using the exact binomial distribution (1), is equal to or higher than 95%.

All other secondary endpoints will be described by vaccine group using descriptive statistical methods, as suggested in Table 5.1.

Immunogenicity endpoints

For all the subjects, a descriptive analysis for pre-Dose 1 (D0), 7 days post-Dose 3 (D14), 14 days post-Dose 4 (D28), and 14 days post-Dose 5 (D42) will present the following statistics for RVNA titers in each vaccine group:

- Number of subjects with RVNA titer available
- Number and percentage of subjects with RVNA titer ≥ 0.2 IU/mL (LLOQ) and 95% CI of the proportion
- Number and percentage of subjects with RVNA titer ≥ 0.5 IU/mL, and 95% CI of the proportion
- Number and percentage of subjects with complete or incomplete results at the starting dilution (1/5) of the RFFIT assay

- Among the analysis population
- Among the subset of subjects with a determined result (identical duplicate values, either Complete or Incomplete)
- GMTs and 95% CI of RVNA titers
- GM of individual titer ratio (GMTR) between the post vaccination time points (D14, D28, and D42) and the baseline (D0) within each group, and the 95% CIs:
 - D14/D0
 - D28/D0
 - D42/D0
- Distribution of titers (minimum, Q1, median, Q3, maximum): based on Log10 transformation first and then antilog transformation.
- Log₁₀ (Titer): mean and its standard deviation (SD)
- Reverse Cumulative Distribution Curves (RCDC) of RVNA titers at D0, D14, D28, and D42.

The complete descriptive immunogenicity data will be analyzed on the per-protocol analysis set (PPAS) primarily.

Safety endpoints

The analysis will be descriptive. The statistics presented in [Table 4.1](#) will be produced, based on the Safety Analysis Set (SafAS).

The safety analysis will report the occurrence of solicited reactions and the incidence of unsolicited AEs including SAEs and AESIs, over the safety observation period according to the vaccine received.

- Immediate unsolicited systemic AEs reported in the 30 minutes after each and vaccination.
- Solicited injection site reactions occurring within 7 days after each injection.
- Unsolicited injection site reactions occurring within 28 days after each injection.

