- Solicited systemic reactions occurring between the first and the second injection, between the second and the third injection, and up to 7 days after the remaining injections.
- Unsolicited systemic AEs occurring between each injection and up to 28 days after the last injection.
- SAEs throughout the trial, ie, up to 6 months after the last injection.
- AESIs throughout the trial, ie, up to 6 months after the last injection.

In order to avoid any under-estimation of the incidences, the number of subjects with documented safety will be used as denominator of the frequencies.

- For solicited reactions, the denominator is the total number of subjects who have non-missing data for the particular category of reaction during the time period concerned.
Note: for solicited systemic reactions, if a reaction is ongoing at the time of the next vaccination, it will be treated differently depending on whether or not it has increased in intensity following the later vaccination.
 - If it has not increased in intensity after the next vaccination, it is to be attributed to the earlier vaccination, and is counted as just a single occurrence in safety analysis. The time of onset is the first day of the first occurrence in the earlier vaccination.
 - If it has increased in intensity after the next vaccination, it will be counted as 2 separate occurrences after each vaccination in safety analysis (the 2 occurrences will be attributed to the earlier vaccination and later vaccination, respectively). The date of the later vaccination will be considered as the end date for the first occurrence and the start date of the second occurrence, respectively.
- For unsolicited events, the denominator is the total number of subjects who were vaccinated at the dose analyzed (for the analyses after each dose) or the total number of subjects who were vaccinated at least one dose (for the analyses after any dose).

For safety parameters, 95% CIs of point estimates of proportion will be calculated using the exact binomial distribution (Clopper-Pearson method) for proportions [\(1\)](#).

30-minutes Post-Vaccination Observation Period

Unsolicited systemic AEs occurring within 30 minutes after each vaccination will be presented in summary safety tables, analyzed according to their causality (relationship to the study vaccine) and Grade 3 intensity.

Solicited Reactions

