Then, in the context of the COVID-19 crisis, enrollment was paused from the 12th of March 2020 and ongoing vaccination were stopped on the 16th of March 2020. Twenty-nine ongoing subjects (from all the 4 groups) are expected to be withdrawn and excluded from the PPAS as they are unable to complete their vaccination schedule as planned in the protocol due to national confinement measures. Still with the aim to secure the study power and maintain the randomization ratio, 30 additional subjects will be enrolled in the study. Finally, 636 subjects are

planned to be enrolled, with a planned overall distribution of 318:106:106:106 among the 4 vaccine groups.

Assuming a proportion of subjects with an RVNA titer ≥ 0.5 IU/mL of 99% in the VRVg-2 + HRIG group, this sample size will give more than 93% of power to demonstrate the superiority of this rate to 95% on the PPAS.

In order to maintain the 3:1:1:1 ratio, the additional arm of subjects receiving VRVg-2 as standalone will include 106 subjects; the results will be descriptive, mainly versus the VRVg-2 + HRIG group. The number of subjects is the same as the 2 controls to facilitate group allocation, and will allow good precision of the results.

The 3:1:1 design is chosen to optimize the non-inferiority testing for immunogenicity with 2 comparators and to increase the size of the safety database of VRVg-2 vaccine.

In case of any new study hold, withdrawn or out of vaccination time windows subjects might be replaced and sample size might be increased accordingly.

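### The SAP's only between-group safety comparison is a 0.05 Fisher test with no risk difference or interval; adding an estimate with a 95% CI would show how large an excess the data cannot exclude

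*SAP*

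**What the plan says.** Protocol 2.2 sets a comparative but descriptive safety objective: "To describe the safety profile of VRVg-2 versus Verorab and Imovax Rabies vaccines when co-administered with HRIG". For the safety endpoints, SAP 4.1.2.2 states "The analysis will be descriptive", and the intervals it plans are for one group at a time: "95% CIs of point estimates of proportion will be calculated using the exact binomial distribution (Clopper-Pearson method) for proportions".

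The one step that sets VRVg-2 against a control is in SAP 4.1.3.1, among the exploratory analyses, at the end of the text on demographic subgroups and center. It begins: "In case of any safety signal detected in the VRVg-2 vaccines, a statistical comparison will be performed". The contrasts are "between VRVg-2 groups (VRVg-2+HRIG and/or VRVg-2) and each of the control groups", and the method is given as "with a Fisher exact test in order to check for statistical significance (alpha=0.05, two sided". The section does not define a signal. It asks for no risk difference, ratio, interval for a difference or upper bound. Protocol section 12 contains no between-group safety test.

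The SAP does specify an interval for a difference of two proportions, the Wilson score method in 4.1.1.2, but only for the D28 immunogenicity endpoint. Group sizes are planned "with a planned overall distribution of 318:106:106:106 among the 4 vaccine groups" (SAP 4.5).

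**The concern.** When a signal arises, the useful question is how large an excess over the licensed vaccines the data allow. The rule answers only whether p is below 0.05. With 106 subjects in each control arm, a non-significant result is the likely outcome for uncommon events even when there is a moderate true excess. Two separate single-group intervals do not give the uncertainty of the difference.

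A significant result is also hard to read. The event is chosen because it looks unusual and is then tested on the same data, against two controls and with one or two VRVg-2 groups. The nominal 0.05 is therefore not its error rate.

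At stake is whether the safety comparison with Verorab and Imovax Rabies rests on an estimate or on a yes/no verdict that carries little information at these sizes.

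**Working it through.** **Inputs.** Planned sizes are 318 (Group 1) and 106 (each of Groups 2, 3 and 4), from SAP 4.5. The test is a two-sided Fisher exact test at 0.05, from SAP 4.1.3.1. The interval is the Wilson score method for a difference, from SAP 4.1.1.2. The event counts and true event rates below are assumptions; neither document gives any for this purpose.

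**The plan's own figures.** These concern immunogenicity only. With 99% in each group, a 5% margin, one-sided 2.5% and 213 against 71 evaluable subjects, the Farrington-Manning power is 90.1% (stated: at least 90%). Inflation gives 213/0.8 = 266.25, rounded up to 267, and 71/0.8 = 88.75, rounded up to 89, as stated. The test against 95% with n = 213 has exact power 93.6% (stated: more than 93%). All reproduce. No power or detectable difference is stated for any safety comparison.

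**Where the Fisher test turns significant, Group 1 against one control.**

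| Group 1 | Control | Two-sided p |
|---|---|---|
| 10/318 | 0/106 | 0.073 |
| 11/318 | 0/106 | 0.073 |
| 12/318 | 0/106 | 0.043 |

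With 1 or 2 control events, Group 1 needs 19 or 24 events respectively.

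**Interval for 11/318 against 0/106.** The difference is 11/318 - 0 = 0.03459. The single-group Wilson limits are l1 = 0.01942 and u1 = 0.06087 for Group 1, and l2 = 0 and u2 = 0.03497 for the control.

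- Lower: 0.03459 - 1.96 × sqrt(0.01942 × 0.98058/318 + 0.03497 × 0.96503/106) = 0.03459 - 0.03812 = -0.0035.
- Upper: 0.03459 + 1.96 × sqrt(0 + 0.06087 × 0.93913/318) = 0.03459 + 0.02628 = 0.0609.

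The 95% CI is therefore -0.35 to +6.09 points, alongside p = 0.073. The planned single-group Clopper-Pearson intervals would show 1.74% to 6.10% and 0% to 3.42%, with no statement about the difference.

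**How often the test is non-significant.** This is an exact enumeration over two independent binomial counts at 318 and 106. A result counts as detected only if p <= 0.05 with the excess in Group 1. The last column counts trials in which the Wilson interval does not lie wholly above zero.

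| True rate, control v Group 1 | Fisher non-significant | Interval not above zero |
|---|---|---|
| 1% v 3% | 91% | 94% |
| 1% v 5% | 60% | 59% |
| 5% v 10% | 69% | 67% |
| 10% v 20% | 33% | 32% |
| 5% v 15% | 17% | 17% |

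For Group 4 against a control (106 v 106), the Fisher figures are 78% for 1% v 5% and 54% for 10% v 20%.

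The two columns nearly coincide, so the low power comes from the sample size and not from the choice of Fisher's test. The two methods can still disagree near the boundary. At 12/318 v 0/106, Fisher is significant while the interval is -0.07 to +6.48 points. At 5/106 v 0/106, Fisher gives p = 0.060 while the interval is +0.31 to +10.57 points.

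**The case against.** The strongest reply is that the test is a small exploratory supplement to a full descriptive analysis. Each group's proportion has an exact interval. Unsolicited events are tabulated by nature, causality, onset, duration and intensity, and SAEs by causality, seriousness and outcome (SAP 4.1.2.2). Causality of SAEs is assessed by the investigator and the sponsor's safety officer (Protocol 10.4), and a safety management team reviews signals (Protocol 1.2 and 3). All of this stands, and it limits the point.

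It also rules out several stronger readings:

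- **That non-significance clears a signal.** A reader might infer this, but no section of either document says so.
- **That a true harm of 11/318 against none would always be missed.** That split is an illustrative observation. If 3.46% and 0% were the true rates, the test would have about 42% power and would be non-significant in about 58% of trials.
- **That any true multi-fold excess would usually be missed.** This fails at commoner rates: 10% v 20% is missed in 33% of trials and 5% v 15% in 17%. Protocol 1.3.2 lists several reactions at 10% or more.
- **That an interval would find more harm.** At 318:106 it excludes zero about as often as Fisher's test reaches significance.

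The miss rates are also unconditional, whereas the test runs only once a signal has been detected. Under one assumed trigger (observed rate at least twice the control rate, with at least 3 events), the 5% v 10% figure falls from 69% to 41%. Because a signal is not defined, the documents support no single conditional figure.

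The reply does not supply a between-group estimate. The only comparative safety step still yields a verdict without an effect size.

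**Conclusion.** The point holds as a low-cost improvement in how a safety signal is reported; it is not an error in the plan. The only between-group safety comparison gives a p-value and no measure of the difference. At the planned sizes that p-value says little for uncommon events: 11/318 v 0/106 is non-significant while an excess of about 6 percentage points is not excluded. The conclusion rests on the planned group sizes (actual safety-set counts per dose will differ), on assumed event rates, and on miss rates that are not conditional on the undefined trigger. The gain from an interval is in interpretation and not in power.

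**What to change.** In SAP 4.1.3.1, replace the bare significance check with wording such as: *For any safety signal, the difference in the proportion of subjects with the event, each VRVg-2 group compared (Group 1 and/or Group 4) minus each control (Group 2, Group 3), will be presented with its two-sided 95% CI by the Wilson score method of Section 4.1.1.2. Interpretation will be based on the estimate and the upper confidence limit. Any Fisher p-value is descriptive, because the event was selected from the same data. A non-significant difference will not be taken as absence of risk.*

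Keeping Group 4 in the wording preserves the contrasts that the section already allows. The SAP's version history places version 1.1 after the first database lock and unblinding, so an addition made after that point should be dated and labelled as post-unblinding.

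The cost is one extra column in tables that are produced only if a signal arises, using an interval already specified for the primary analysis. No confirmatory test or alpha changes, and no new data are needed. The downside is that wide intervals will show openly how little excess the trial can exclude for uncommon events.

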4.1.3.2 Impact of the COVID-19 pandemic

To evaluate the possible impact of the COVID-19 pandemic on the study conduction, main immunogenicity and safety results, the following sensitive analyses will be performed but not limited to:

- Impact of COVID-19 pandemic on subject's disposition, based on enrolled subjects
Note: Subjects impacted by COVID-19 pandemic situation correspond to subjects with at least one major/critical protocol deviation due to COVID-19 or who did not complete the study due to COVID-19 or who reported an impact on 6-month follow up in pandemic form
- Impact of COVID-19 pandemic on immunogenicity analysis, based on FASI.
- Impact of medical history of suspected/confirmed COVID-19 pandemic before enrollment on immunogenicity analysis, based on FASI.
- Impact of the use of concomitant medications that are used during the study/ or were used not over 2 months before enrollment for treating/preventing COVID-19 (ie, Hydroxychloroquine and chloroquine) on immunogenicity based on FASI.
- Immunogenicity of subjects who did not take any concomitant medications for treating/preventing COVID-19 (ie, Hydroxychloroquine and chloroquine) within 2 months before enrollment based on PPAS
- Impact of COVID-19 pandemic on safety overview up to 28 days after any vaccination, based on SafAS.
- Impact of medical history of suspected/confirmed COVID-19 before enrollment on safety overview up to 28 days after any vaccination, based on SafAS.
- Impact of the use of concomitant medications that are used during the study/ or were used at least 2 months before enrollment for treating/preventing COVID-19 (ie, Hydroxychloroquine and chloroquine) on safety overview up to 28 days after any vaccination, based on SafAS.

Note: If only few subjects were impacted by COVID-19 (<5% in randomized subjects), only the corresponding listings will be provided instead of tables for immunogenicity and safety evaluation. Exception is the immunogenicity evaluation for the subjects who did not take any concomitant

medications for treating/preventing COVID-19 (ie, Hydroxychloroquine and chloroquine) within 2 months before enrollment base on PPAS.

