before and during data collection should be clearly reported due to the possible interference with rabies vaccines (22, 27). Exceptionally, dosage may be collected for these medications.

The information reported in the CRB for each reported medication will be limited to:

- Trade name
- Origin of prescription: prophylaxis Yes/No. Medication(s) prescribed for AE prophylaxis will be recorded in the Action Taken of the AE collection tables.
- Medication category (1, 2, or 3)
- Start and stop dates

Dosage^a and administration route, homeopathic medication, topical and inhaled steroids, as well as topical, ophthalmic, and ear treatments will not be recorded. Topical analgesics should not be applied at the site of vaccination; however, if they are applied inadvertently to the vaccination site, they should be recorded as a Category 1 medication in this specific instance.

Medications given in response to an AE will be captured in the “Action Taken” section of the AE CRF only. No details will be recorded in the concomitant medication CRF unless the medication(s) received belongs to one of the prelisted categories. Medications will not be coded.

7 Management of Samples

Blood samples for the assessment of antibody responses will be collected at V01, V04, V05, and V06. See the Table of Study Procedures and [Section 5.1.3](#) for details of the sampling schedule.

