4.2.2 Per-Protocol Analysis Set

The PPAS is a subset of the FAS.

As D28 is the timepoint used for primary objective assessment, the PPAS will be defined at D28 (V05). The subjects presenting with at least one of the following relevant protocol deviations before D28 (ie, 14 days after the fourth vaccine injection) will be excluded from the PPAS:

- Subject did not meet all protocol-specified inclusion criteria or met at least one of the protocol-specified exclusion criteria
- Subject did not receive the first 4 doses of the vaccination schedule
- Subject received a vaccine other than the one that he / she was randomized to receive
- Preparation and / or administration of vaccine and concomitant medication (including HRIG for groups 1 to 3) was not done as per-protocol for the first 4 vaccinations
- Subject did not receive the first 4 vaccine injections in the proper time window
 - Vaccination 2 in [D03-D05]
 - Vaccination 3 in [D07-D09]
 - Vaccination 4 in [D13-D16]
- Subject did not provide the post-Dose 4 serology sample at V05 in the proper time window [D25-D31] from D0

- Subject received a protocol-prohibited therapy/medication/vaccine (belonging to categories 2 and 3) before V05
- Subject's serology sample is missing or did not produce valid test results at D0 or D28
- Seropositive subject at D0, ie, RVNA titer \geq LLOQ
- Subject developed a protocol-specified withdrawal criterion during the study but was not withdrawn
- Subject did not receive the correct amount of HRIG at D0

Adherence to the definition of the PPAS analysis set may also be decided during the blinded data review, ie, before breaking the code and locking the database.

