4.2.5 Populations Used in Analyses

The following table presents populations used in the statistical analysis.

Table 4.5: Populations used in the analyses

		Analysis sets	Analysis by
Primary Objective	D28 non-inferiority testing	PPAS (main analysis), FAS/FASI	Received vaccine group Randomized vaccine group
Secondary Objectives	D28 Superiority testing	PPAS (main analysis), FAS/FASI	Received vaccine group Randomized vaccine group
	Immunogenicity description	PPAS (main analysis), FAS/FASI	Received vaccine group Randomized vaccine group
	Safety description	SafAS	Received vaccine group
Exploratory analyses	Main immunogenicity endpoints	FASI (main analysis) PPAS*	Randomized vaccine group Received vaccine group
	Main safety endpoints	SafAS	Received vaccine group

*Note: Immunogenicity of subjects who did not take any concomitant medications for treating/preventing COVID-19 (ie, Hydroxychloroquine and chloroquine) within 2 months before enrollment

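### The always-tabulated chloroquine/hydroxychloroquine analysis defines non-users by pre-enrollment use only, and it is not settled whether the PPAS removes subjects who take these drugs during the vaccination course

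*SAP*

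**What the plan says.** SAP 4.1.3.2 lists two immunogenicity analyses concerned with chloroquine and hydroxychloroquine.

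- The FASI analysis looks at the impact of "concomitant medications that are used during the study/ or were used not over 2 months before enrollment". It counts exposure on study as well as before it.
- The PPAS analysis is restricted to non-users, and its window is only the time before enrollment: "subjects who did not take any concomitant medications for treating/preventing COVID-19 (ie, Hydroxychloroquine and chloroquine) within 2 months before enrollment based on PPAS". The note under Table 4.5 (SAP 4.2.5) repeats that window: "Immunogenicity of subjects who did not take any concomitant medications for treating/preventing COVID-19 (ie, Hydroxychloroquine and chloroquine) within 2 months before enrollment".

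The same section sets a reporting rule: "If only few subjects were impacted by COVID-19 (<5% in randomized subjects), only the corresponding listings will be provided instead of tables". One analysis is exempt: "Exception is the immunogenicity evaluation for the subjects who did not take any concomitant" such medication, again with the pre-enrollment window and the PPAS.

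Protocol 6.9 gives chloroquine and hydroxychloroquine as an instance of drugs that interfere with the immune response. It says that use "before and during data collection should be clearly reported due to the possible interference with rabies vaccines". Reportable medications are collected from V01 to V07.

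PPAS membership is decided separately. SAP 4.2.2 and Protocol 12.2.3 exclude a subject on this ground: "Subject received a protocol-prohibited therapy/medication/vaccine (belonging to categories 2 and 3) before V05". Both also allow PPAS adherence to be decided at the blinded data review.

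**The concern.** The non-user analysis should show whether the D28 result holds in subjects free of a drug that the protocol says may interfere with the vaccine. Its definition uses only the part of the exposure window before enrollment. A subject with no earlier use who starts the drug on D1 and continues to D28 meets the definition.

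The analysis that does count on-study use can be reduced to a listing, while the one certain to be tabulated does not count it. If an in-course user is in the PPAS, a low D28 titer in that subject remains in both the main analysis and the check on it. With about 71 evaluable subjects in each control group, one control response is worth 1/71 = 1.4 percentage points against a 5-point margin.

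**Working it through.** **1. The plan's own figures.** These are background, and nothing in this point disputes them. Inputs from SAP 4.5 are 99% response in all three groups, a 5% margin, one-sided 2.5% and 3:1 allocation.

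- Farrington-Manning power at 213/71 is 90.1% per comparison. Treating the two comparisons as independent, 0.9008² = 81.2% overall.
- Inflation for 20% not evaluable: 213/0.8 = 266.25, rounded up to 267; 71/0.8 = 88.75, rounded up to 89.
- The exact test against 95% at n = 213 needs at least 209 responders and has 93.6% power.

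All agree with the stated values, so 213:71 is a fair base for illustration.

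**2. Which subjects each rule catches.**

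| Use of the drug | FASI impact analysis | PPAS non-user filter | PPAS medication criterion |
|---|---|---|---|
| Within 2 months before enrollment | counted | removed | not clearly addressed |
| D0 to before V05 | counted | not removed | removed only if the drug is protocol-prohibited and in category 2 or 3 |
| V05 to V06 | counted | not removed | not reached |

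The second row turns on whether these drugs are prohibited. They are absent from the exclusion criteria (Protocol 5.2.5) and the contraindications (5.2.7). Protocol 6.9 calls its categories reportable, not prohibited, and the category 2 examples do not name these drugs. Category 2 is nevertheless defined by possible effect on the immune response, which fits them. Removal is therefore possible but not assured. The third row does not depend on that question: the criterion stops at V05, so the D42 description is not covered.

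**3. When the listing rule applies.** 5% of 636 is 31.8. With 31 impacted subjects the share is 31/636 = 4.9%, so the FASI analysis would be a listing only.

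**4. Illustration of size.** The number of in-study users is not given, so this is an assumed case: one control failure is an in-study user, is still in the PPAS, and is then removed. The interval is the one in SAP 4.1.1.2:

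L = (p1 − p2) − z·√[ l1(1 − l1)/n1 + u2(1 − u2)/n2 ], with z = 1.96, l1 the lower Wilson limit in Group 1 and u2 the upper Wilson limit in the control.

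Five Group 1 failures:
- Before removal: p1 = 208/213 = 97.65%, p2 = 70/71 = 98.59%, l1 = 94.62%, u2 = 99.75%. The square-root term times z is 3.24%, so L = −0.94% − 3.24% = −4.18%.
- After removal: p2 = 70/70 = 100% and u2 = 100%. The term is 3.03%, so L = −2.35% − 3.03% = −5.38%.

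| Group 1 failures of 213 | L with 1/71 control failures | L with 0/70 | Conclusion |
|---|---|---|---|
| 3 | −2.89% | −4.06% | unchanged, non-inferior |
| 4 | −3.55% | −4.73% | unchanged, non-inferior |
| 5 | −4.18% | −5.38% | changes |
| 6 | −4.80% | −6.01% | changes |
| 7 | −5.41% | −6.63% | unchanged, not demonstrated |

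At a true 99% in both groups, 5 or 6 failures in 213 has probability 5.8%, and exactly one in 71 has 35%. The product is 0.058 × 0.35 ≈ 2% per comparison, before requiring that the control failure be an in-study user in the PPAS.

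**5. The other direction.** If the user is one of 7 Group 1 failures, removal gives 6/212 against 1/71, and L moves from −5.41% to −4.83%. Here the correction helps VRVg-2.

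**The case against.** The strongest reply is that the PPAS already deals with on-study use. Category 2 has an open list, Protocol 6.9 cites these two drugs as interfering with the immune response, and no separate list of prohibited drugs is supplied, so the category may be what gives the criterion its content. On that reading the D1-to-D28 user has left the PPAS, and the non-user filter need only handle earlier use. It would also explain why the FASI bullet, whose set has no medication exclusion, names on-study use and the PPAS bullet does not. This reply stands far enough to rule out a stronger reading that a reader might infer: that in-course users stay in the PPAS. The documents do not say so. Equally, they do not say that such users leave it, and the reply does nothing for use between V05 and V06.

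Second, a listing would still show each in-study user, and with few users their individual D28 results can be read directly. That stands. The gap is in one analysis, and the plan as a whole is not blind to on-study use.

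Third, the illustration is a selected case, and the analysis is exploratory and descriptive. Both are true. They limit the size of the point and make formal non-inferiority testing in this subset unnecessary.

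**Conclusion.** The point holds as a defect of definition in one exploratory analysis. The set meant to represent subjects free of these drugs can include subjects who took them during the course, and whether it does depends on an unstated classification or on a decision at blinded review. For D42 the gap exists however the drugs are classified.

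The size is unknown and may be nil, because the number of in-study users is not given. A reader might infer that the omission favours VRVg-2. The documents do not support a fixed direction: if use is independent of arm, 3:1 allocation makes a user three times as likely to be in Group 1 as in a given control group, and a drug-related failure there counts against VRVg-2. The 213:71 figures assume one control failure and one removed subject, and show a changed conclusion only at 5 or 6 Group 1 failures. The primary endpoint, the decision rule and the sample-size figures are unaffected.

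**What to change.** In SAP 4.1.3.2 (the bullet and the exception note) and in the Table 4.5 note, define the set as PPAS subjects with no recorded chloroquine or hydroxychloroquine from 2 months before enrollment through the V05 sample, and through V06 for D42 results. In SAP 4.2.2, state whether these drugs count under the PPAS medication criterion. Showing the two difference intervals descriptively in this set is optional.

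The SAP's version history places version 1.1 after the first database lock and unblinding, so a change made now should be labelled as made after unblinding. The cost is a sentence, a table note and one clarification. Protocol 6.9 already requires the data. The only downside is a slightly smaller exploratory set.
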